#### **4.3.4 Demographics**

The following demographic characteristics data will be collected on the 'Demography at Screening visit (Visit 1)' eCRF page at Screening Visit 1 Day -6 to -1:

- Year of birth
- Age
- Sex
- Race
- Ethnicity
- Country
- Height (cm)
- Weight (kg)
- Body mass index (BMI) (kg/m^2)

Weight, height and BMI will be collected on the 'Demography - Post Screening at Day 0, Day 28, Day 42, Day 84, Day 126, Day 168. Additionally, Demography will be assessed on Follow Up Visit, Unscheduled\_visit' for both Groups 1 and 2 (subjects not entered in Stage 3). During Stage 2 these assessments will be performed on the day of the maintenance dose. For subjects entered in Stage 3, demography parameters are additionally measured at the final assessment, i.e., occurring 1 week after last Stage 3 visit or ≥28 days after last injection for EW (Early Withdrawal). This is in accordance with the schedule of events table 16 (in Protocol).

Age (in years) at Screening will be recorded as a whole integer.

Weight will be measured and recorded in kilograms (kg). Height will be measured in centimetres at the screening visit (Visit 1) only.

Missing demography data will not be imputed.

The analysis will be summarised for Safety, Intention-To-Treat & Per-Protocol populations as defined in Section 3.

---

Document:

C:\ProgramData\activePDF\Temp\DocConverter\API\Input\\$651f4dc0b253\$FE3041C5883446E892B20AB6D3F0E1BD.docx

Author: [name]

Version and Date: Version 1.0, 21 Apr 2023

Page 46 of 66

**4.3.5 Medical History**

General medical history findings in the past 5 years, considered relevant to the study by the investigator, will be documented in the eCRF together with the respective dates and periods (it should be indicated whether the condition is a past or an ongoing disease/illness at study entry). Relevant findings include, but may not be limited to, major surgeries, heart diseases, respiratory diseases, central nervous system and neurological diseases, psychiatric disorders, blood disorders, hepatorenal disorders, genitourinary disorders, and known allergies.

**4.3.5.1 Coding of Medical History Terms**

The medical history term (Investigator term) is assigned to the LLT, and a PT will be classified by a HLT, a HLGT and a SOC according to the MedDRA thesaurus, Version 25.0.

Although there can be multiple SOCs for a PT, each PT will be linked with one SOC, namely the primary SOC which is automatically assigned by MedDRA via one HLT, HLGT route.

The following coding data will be presented:

- LLT
- PT
- Coding data per primary SOC:
  - HLT
  - HLGT

Medical history will be reported on a per-subject basis. This means that even if a subject suffered the same clinical event repeatedly (i.e., events mapped to the same PT) the event will be counted only once and the earliest date will be regarded as start date of the event and the latest date will be regarded as stop date of the event.

The same rule for counting applies for PTs mapped to the same HLT and for HLTs mapped to the same HLGT and for HLGTs mapped to the same SOC.

**4.3.6 Prior and Concomitant Medications**

Concomitant medications include all medications that a subject used at any stage during the study. Any medication started prior to or any time after the first study medication administration, thus after the Baseline visit, will be included.

Concomitant medications data will be collected throughout the study on the 'Prior and concomitant Medication and Therapy' CRF page.

Missing concomitant medications data will be handled according to the rules specified in Section 5.3.2.4.

Any concomitant therapies and medications administered during the trial must be documented. This also includes any non-medicinal treatment and hormonal contraception. The following details must be given nature of the disease (indication), date of diagnosis, name of medicine (including active ingredient(s)) or specification of measures, dosage, route of administration and the dates of the start and end of the treatment.

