- Date and time of day when the medication was administered
- Documentation of changes in concomitant diseases and/or concomitant therapies (also medication taken only once and any non-prescription medicine)
- AEs (for definition see Section 6.3.7)
- Physical examination
- 12-Lead ECG
- Safety laboratory tests (fasted (≥8 hours))
- Vital signs
- Blood sampling for PK, PSA, and PD analysis (before administration of teverelix TFA) (see Table 15 and Error: Reference source not found)
- Pre-dose blood sampling for cardiac biomarkers (Group 2 only)
- ISI
- Administration of the maintenance dose of teverelix TFA, which consists of an SC injection

7.2.4 Follow-up Visit (28 Days after Last Dose)(Group 1 and Group 2 subjects without Stage 3)

At the final visit, the following examinations will be carried out and/or documented:

- Date of visit
- Documentation of changes in concomitant diseases and/or concomitant therapies (also medication taken only once and any medicine taken without a prescription)
- AEs
- Physical examination
- 12-Lead ECG
- Safety laboratory tests (fasted (≥8 hours))
- Blood sampling for PK, PSA, and PD
- Blood sampling for cardiac biomarkers (Group 2 only)
- ISI
- Vital signs
- Demography (only weight)
- Final assessment by investigator and participant

7.2.5 Follow-up Visits (starting 35 days after Last Dose)(Group 2 with Stage 3 subjects only)

Five weeks after the Day 168 maintenance dose injections (Day 203), subjects will attend the clinic and the following procedures will be done:

- Date of visit
- Documentation of changes in concomitant diseases and/or concomitant therapies (also medication taken only once and any medicine taken without a prescription)
- AEs
- Blood sampling for PK, PSA, and PD (local AND central lab serum T levels)

Subjects will continue to attend the clinic every 7 days where the above procedures will be done. Weekly visits will continue until Day 252 or until serum T levels (local lab result) are ≥ 1 ng/mL (local lab result) when the subject will attend the clinic 7 days later and the following procedures will be done:

- Date of visit
- Documentation of changes in concomitant diseases and/or concomitant therapies (also medication taken only once and any medicine taken without a prescription)
- AEs
- Physical examination
- 12-Lead ECG
- Safety laboratory tests (fasted (≥8 hours))
- Blood sampling for PK, PSA, and PD
- Blood sampling for cardiac biomarkers (Group 2 only)
- ISI
- Vital signs

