#### **3.5 Non-missing Central Lab Serum T Record at Day 28 (Lab Serum T Day 28) Analysis Set**

All participants included ITT analysis set, except for patients who received concomitant medications and herbal supplements that could possibly affect T levels, will be included in the Lab Serum T Day 28 analysis set.

If at the time of analysis this population is the same as the ITT population the analysis is conducted on, then results will not be repeated where the same question has been asked for the ITT population.

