#### **4.3.3 Protocol Violations**

Protocol violations are defined as violations that might affect the efficacy or treatment of a subject, and lead to the exclusion of subjects from the analysis sets defined in Section 3.

The following protocol deviations lead to the exclusion from the defined analysis sets:

- Subject did not provide informed consent.
- Subject was not allocated to one of the treatment groups.
- Subject did not take at least one dose of the study medication.
- Prohibited Concomitant Medication received.
- Study visit was outside the permitted window.

The eligibility of all subjects for entry into the study was assessed at Visit 1 Day -6 to -1. A subject should have met all of the inclusion, and none of the exclusion criteria before entry into the study.

The inclusion criteria comprise the following:

1. Is male, aged  $\leq 85$  years ( $\geq 18$  years) at the beginning of the treatment period (Day 0)
2. Has histologically proven advanced adenocarcinoma of the prostate (metastatic or non-metastatic, hormone-sensitive, non-curative), suitable for androgen deprivation therapy
3. Is treatment naïve for any of the following:
  - a. GnRH analogues,
  - b. Androgen receptor antagonists, or
  - c. Androgen synthesis inhibitors (e.g., abiraterone)
4. Agrees to practice contraception during the entire study treatment period and for 3 months after the last dose of IMP is administered:
  - a. Either by using double barrier contraception,
  - b. or, is truly sexually abstinent, when this is in line with the preferred and usual lifestyle of the participant

**Note:** *Periodic abstinence [e.g., calendar, ovulation, symptothermal, postovulation methods for the female partner with childbearing potential] and withdrawal are not acceptable methods of contraception.*

5. Has provided written (personally signed and dated) informed consent before completing any study-related procedure, which means any assessment or evaluation that would not have formed a part of his normal medical care.

The exclusion criteria comprise the following:

---

Document:

C:\ProgramData\activePDF\Temp\DocConverter\API\Input\\$651f4dc0b253\$FE3041C5883446E892B20AB6D3F0E1BD.docx

Author: [name]

Version and Date: Version 1.0, 21 Apr 2023

Page 44 of 66

1. Has abnormal screening and/or baseline laboratory values that suggest a clinically significant underlying disease, or the following laboratory values:

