#### **6.8.3      Supplementary FDA Recommended Efficacy Analyses**

Supplementary analysis will be conducted utilizing the Kaplan-Meier technique to estimate the proportion of patients who achieve and maintain castrate T levels (<0.5 ng/mL or 1.73 nmol/L) from Day 28 through the end of the treatment period using the ITT population.

Treatment failure [non-castrate serum T levels ( $\geq 0.5$  ng/mL or 1.73 nmol/L) with central lab] will be defined as the analysis event.

The following patients will be considered as experiencing an event

1. Patients who did not achieve castrate serum T levels (<0.5 ng/mL or 1.73 nmol/L) by Day 28. Day 28 will be considered as the day of event.
2. Patients who successfully achieve a castrate serum T level by Day 28 but fail to maintain it throughout the treatment period. Day of failure (day of sampling) will be considered as the day of event.

---

Document:

C:\ProgramData\activePDF\Temp\DocConverter\API\Input\\$651f4dc0b253\$FE3041C5883446E892B20AB6D3F0E1BD.docx

Author: [name]

Version and Date: Version 1.0, 21 Apr 2023

Page 62 of 66

The following patients will not be considered as having experienced an event:

[figure not shown]
- 1 Patients who achieve and maintain castrate serum T levels with central lab from Day 28 through the end of the treatment period.
- 2 Patients who leave the trial for reasons other than a non-castrate serum T levels.

Censoring and handling of missing data rules will be used for this analysis:

[figure not shown]
- 1 Patients who achieve and maintain castrate serum T levels with central lab from Day 28 through the end of the treatment period will be censored at their last serum T level assessment.
- 2 Patients who leave the trial for reasons other than a non-castrate serum T level will be censored at their last serum T level assessment.
- 3 Patients with one or more consecutive missing serum T levels and a non-castrate serum T level after the missing time point(s) will be considered to have had an event (treatment failure) at the first missing time point. For example: if the subject's data is missing for Days 28 and 35 and having a non - castrate T levels ( $\geq 0.5$  ng/mL) on Day 42 we should consider that the subjects had an event on day 28.

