**Sensitivity Analyses on Supplementary FDA Recommended Efficacy Analyses**

Two sensitivity analysis will be performed. In the first sensitivity analysis the definition of treatment failures will be expanded and include following patients as treatment failures (patients with event):

1. Patients who did not achieve castrate serum T levels (<0.5 ng/mL or 1.73 nmol/L) by Day 28.
2. Patients who successfully achieve a castrate serum T level by Day 28 but fail to maintain it throughout the treatment period.
3. All the patients who leave the trial will be considered to have had an event at their last serum T level assessment.
4. Patients with two or more consecutive missing T levels (regardless of T levels before and after those missing time points). They will be considered to have had an event at the first missing time point.

In the second sensitivity analysis the ITT population will be changed to the population of patients who have received any dose of IMP and have a non-missing central lab serum T record at Day 28 except for patients who received concomitant medications and herbal supplements that could possibly affect T levels.

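### The medication exclusion in the second Kaplan-Meier sensitivity analysis has no time limit, so men can be removed for treatment started after their outcome

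*SAP*

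**What the plan says.** SAP 3.5 forms the Lab Serum T Day 28 set by taking the ITT set "except for patients who received concomitant medications and herbal supplements that could possibly affect T levels". It gives neither a time window nor a list of drugs.

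The supplementary analysis in SAP 6.8.3 estimates the proportion of men who reach and hold castrate T "from Day 28 through the end of the treatment period using the ITT population". Its event is a central-laboratory T of 0.5 ng/mL or more. For the second of two sensitivity analyses, the SAP states: "In the second sensitivity analysis the ITT population will be changed to the population of patients who have received any dose of IMP". A Day 28 central T record is also required, and the medication exclusion is repeated, again without timing.

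SAP 4.3.6 holds the only definition of concomitant medication. Its first sentence is "Concomitant medications include all medications that a subject used at any stage during the study". Its second is "Any medication started prior to or any time after the first study medication administration, thus after the Baseline visit, will be included". Section 3.5 does not cross-refer to 4.3.6.

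Medication is still recorded after treatment ends. Protocol 7.2.4 (the 28-day follow-up) and 7.2.5 (the Stage 3 visits and final assessment) both list "Documentation of changes in concomitant diseases and/or concomitant therapies (also medication taken only once and any medicine taken without a prescription".

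**The concern.** The set is evidently meant to show that castration was produced by teverelix and not by something else the man was taking. For that purpose, only medication taken before the T result being judged is relevant.

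As written, the rule also catches medication that cannot have influenced the result. Two routes matter:

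- A man withdrawn for local T above 2 ng/mL may start another androgen-deprivation drug that is recorded at his last visit. The drug is a consequence of his failure, yet it removes both his event and his place in the denominator.
- A man who stayed castrate to Day 168 may start other treatment during follow-up. The analysed period is over, yet he is removed too.

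Either way, membership of the set depends on what happened after the outcome. The supplementary analysis was added after discussion with the FDA (SAP 7.1). Its sensitivity analysis should test confounding by other drugs, not be shaped by later treatment.

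**Working it through.** **1. The plan's own figures.** The documents give no figure for this exclusion. The nearest are the intervals in Protocol 8.1.12. The exact (Clopper-Pearson) 95% interval for 54/60 is 79.5% to 96.2%, against a stated (79,96). For 45/50 it is 78.2% to 96.7%, against (78,97). Both reproduce, so the same method is used below.

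**2. Can the exclusion follow the outcome?** Setting the texts side by side:

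- Local T above 2 ng/mL leads to withdrawal (Protocol 4.3 and 5.5).
- Concomitant therapy is recorded at the visits after withdrawal or after Day 168 (Protocol 7.2.4 and 7.2.5).
- SAP 4.3.6 counts anything used at any stage of the study.
- SAP 3.5 and 6.8.3 drop the whole man.

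No step compares the drug's start date with the date of the T result. On the literal reading, the answer is yes.

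**3. Size, with assumed inputs.** Take N = 60 men (the Group 2 enrolment target) and f = 6 failures. Six is the most that the Group 2 stopping rule allows before enrolment ends (Protocol 3.1). That rule counts local T above 2 ng/mL or withdrawal, not the analysis event, so 6 is only a convenient assumption. Assume no censoring, so that the Kaplan-Meier estimate at the end of treatment equals the crude proportion. Let a be the failures removed and b the successes removed:

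rate = (N − f − b) / (N − a − b)

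| Removed | Rate | Exact 95% CI |
|---|---|---|
| none | 54/60 = 90.0% | 79.5 to 96.2 |
| 1 failure | 54/59 = 91.5% | 81.3 to 97.2 |
| 3 failures | 54/57 = 94.7% | 85.4 to 98.9 |
| 6 failures (ceiling) | 54/54 = 100% | 93.4 to 100 |
| 6 successes | 48/54 = 88.9% | 77.4 to 95.8 |
| 3 failures and 3 successes | 51/54 = 94.4% | 84.6 to 98.8 |

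With 50 men and 6 failures, the rate is 44/50 = 88.0% (75.7 to 95.5) with none removed and 44/47 = 93.6% (82.5 to 98.7) with 3 failures removed.

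**4. Direction.** Rearranging the formula, the rate rises when a/(a + b) exceeds f/N and falls when it is below. Here f/N = 6/60 = 10%. As a check, removing 3 failures and 27 successes gives 27/30 = 90.0%, which is unchanged.

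**5. After the fix.** No one is removed for treatment begun after failure, so the example stays at 54/60 = 90.0% (79.5 to 96.2).

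**The case against.** The strongest reply is that the effect is narrow and perhaps rare.

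- Section 3.5 does not point to 4.3.6, and a drug started after a failing sample cannot have affected that sample. A sensible programmer might apply a time limit unprompted. However, the wording in 3.5 describes the kind of drug, not when it was taken, and 4.3.6 is the only definition on offer. The literal reading is the natural one.
- The window for recording a switch is short. A Day 21 failure has his safety follow-up on Day 28. The later local T checks fall 35 days after the previous dose (35 − 0, 77 − 42, 119 − 84, 161 − 126), so a 28-day follow-up is already due. This stands and keeps the likely numbers small. It does not close the gap. The documents differ on follow-up after early withdrawal (28 days in Protocol 4.3 and 5.1, at least 28 in the synopsis, more than 28 in SAP Table 4) and need reconciling, and the SAP sets no cut-off on the drug's start date.
- The other analyses keep these men. This stands. The main Kaplan-Meier analysis uses ITT, the first sensitivity analysis counts every leaver as an event, and the primary endpoint's sensitivity analysis uses ITT.

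A reader might infer more than the documents support:

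- *The analysis loses all its failures.* It does not. A man with central T of 0.5 ng/mL or more but local T of 2 ng/mL or less is not withdrawn on T grounds. Other androgen deprivation is prohibited while he is on study, so he normally remains in the set as a failure.
- *The per-protocol set is affected in the same way.* SAP 4.3.3 does list "Prohibited Concomitant Medication received" as grounds for exclusion, also without timing. But the PP set requires completing the study (SAP 3.7), so a man withdrawn for T above 2 ng/mL is already outside it.
- *The shift could carry the result across the 90% target.* That target concerns the Day 28 response and the Group 1 enrolment rule. No decision rule applies it to this maintenance analysis.
- *Men with permitted past finasteride would be dropped.* Finasteride stopped before the washout was not used during the study, and SAP 6.6 summarises prior and concomitant medication separately. The phrase about starting before the first dose most naturally covers drugs still in use.

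**Conclusion.** The concern holds for one analysis. The exclusion in SAP 3.5, as used in the second sensitivity analysis of 6.8.3, has no time limit. Followed as written, it removes men for treatment begun after a recorded T failure or after the analysed period, which is selection on a post-outcome event.

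The size cannot be known from the documents. In the example, losing half of the failures adds 4.7 points (90.0% to 94.7%), and losing six men who stayed castrate takes off 1.1 points (90.0% to 88.9%). These figures rest on an assumed 60 men, 6 failures, no censoring and an assumed number removed. The number removed is probably small. No claim about the primary result follows from this point. What suffers is the meaning of a check that should be independent of later treatment.

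**What to change.** In SAP 3.5 and in the second sensitivity analysis of 6.8.3, tie the exclusion to dates:

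- Exclude a man only if a T-affecting drug or supplement was in use on or before his Day 28 sample. Use that ended before the first dose should count only if it breached a stated entry restriction, such as the pre-screening washouts of 12 weeks for finasteride and 25 weeks for dutasteride. A window opening at Day 0 would wrongly keep men who breached those washouts.
- If such a drug was started after Day 28, while the man was still castrate and within the treatment period, keep him and censor at its start date.
- Ignore any such drug started after a recorded T failure or after the analysed period ends.

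The cost is SAP wording. Start and end dates of all medication are already required (Protocol 5.8, SAP 4.3.6), so no new data are needed. The downside is that a few more men stay in the set and its rate may look less favourable. Under SAP 7.2 the SAP is not changed after database lock. If lock has passed, the dated version should be reported and justified in the clinical study report.

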**4.3.6.1 Prohibited Previous and Concomitant Treatments**

In line with the inclusion and exclusion criteria, during the study the use of the following drugs is prohibited:

- Antiarrhythmic medications
  - Class IA (e.g., quinidine, procainamide)
  - Class III (e.g., amiodarone, sotalol)

---

Document:

C:\ProgramData\activePDF\Temp\DocConverter\API\Input\\$651f4dc0b253\$FE3041C5883446E892B20AB6D3F0E1BD.docx

Author: [name]

Version and Date: Version 1.0, 21 Apr 2023

Page 47 of 66

- Anti-androgen therapy (e.g., T replacement therapy, and 5α-reductase inhibitor treatment etc) (Spironolactone is a permitted concomitant treatment)
- GnRH analogue or antagonists
- Androgen receptor antagonist
- Androgen synthesis inhibitors (e.g. abiraterone)
- Any other medication (e.g., 5-alpha reductase inhibitors) or herbal product (e.g., St. John's wort) that may affect hormone levels and might, therefore, confound interpretation of study results
- Finasteride and dutasteride within 12 weeks and 25 weeks, respectively, prior to screening

#### **4.3.6.2 Admissible concomitant treatments**

All other medicines, as well as over-the-counter medicines, apart from those mentioned in the prohibited treatments are allowed provided they do not affect the primary endpoint or integrity of this study.

This applies also specifically to following treatment options for prostate cancer:

- Prostate surgery
- Radiation therapy (discuss with Antev medical monitor prior to inclusion)
- Chemotherapy
- Cryotherapy
- Immunotherapy

#### **4.3.6.3 Coding of Concomitant Medication Terms**

Concomitant medications are classified according to active drug substance using WHODD GLOBAL B3 Version Sep 2020.

The WHO-DD drug identity (ID) has 11 characters. The preferred name, for example, the salt/ester of the substance is defined by the first 8 characters, and the WHO-DD name is defined by the 11 characters.

In addition, the Anatomical Therapeutic Chemical (ATC) classes are assigned to the drug ID. An ATC code has 7 characters. The first character gives the anatomical main group (1st level), the first 3 characters give the therapeutic main group (2nd level), the first 4 characters give the therapeutic subgroup (3rd level), the first 5 characters give a further level therapeutic subgroup (4th level), whereas the 7 characters give the subgroup for the chemical substance. In this study, ATC codes are defined to the 4th level.

Although there can be multiple ATC classes for a drug, each drug will be linked with one ATC class which will be assigned manually during the coding process, based on information about the indication and route in relation to the study therapeutic area. This one ATC class will be indicated as the 'primary' ATC class, and only the primary class will be presented.

